An Internet Based Adaptation of a Divorce Intervention Beginnings Program for
Divorced Parents

NCT05209932

December 27, 2022

Study Protocol. The protocol is described as it was presented in the grant application. However, due to the COVID pandemic the trial was much more difficult to conduct than anticipated. In order to preserve our ability to implement the RCT, the scope of the trial was modified to have a reduced number of participants and to drop the follow-up assessment while preserving random assignment and responses from both children and parents. These changes were approved by our program officer. We also changed the comparison condition from an internet program comparison to a waitlist control condition because we felt that the latter is a more ecologically valid comparison.

Recruitment and Procedures. Qualtrics leading-edge sample acquisition technology will be used to recruit 360 parents from a nationally representative sample of divorced parents that includes the same percentages of ethnic groups as in the US Census data.

Initial sampling criteria will include: divorced, separated but never married, divorcing or separating; has one child or more between 6 and 18, and English speaking. As in our effectiveness trial, both mothers and fathers as well as separating parents who were never legally married will be eligible to participate. Parents who meet initial sampling criteria will be sent an email with further information about the study including a link to a video invitation to participate in the study. Parents will complete a web-based survey including questions about contact level with child/ren (to be eligible parents need to have a minimum amount of contact defined as at least three hours/week or at least one overnight every other week) and access to a computer with high-speed internet or a smart phone. We will receive a list with phone numbers and email addresses of parents who fully meet the above criteria and are interested in participating in the study. A research specialist will contact parents by phone to provide details of the study (e.g., random assignment, compensation), rescreen for eligibility and have parents complete a consent form using Konexx, a leading voice-recording product.

Parents with offspring ages 11 to 18 will be asked to provide permission for them to participate in assessments. Based on our previous randomized trials with divorced families, we anticipate there will be 1.5 children/family who are between 6 and 18 years old, giving a total of 540 children. We anticipate that 50% of the offspring will be 11 or older, giving a possible total of 270 adolescent reports.

Offspring ages 11-18 whose parents provide permission for them to participate in the assessments will be called by a research specialist who will explain the nature of their participation and have the adolescent complete one of two developmentally appropriate assent forms (11-13; 14-17) or consent (18) form using Konexx. After the consent/assent process has been completed, parents and youth will be emailed a web link to access the pretest. After this link is sent, parents and youth will receive up to three email reminders (every 2 days) about completing the pretest. The assessments will be 15 minutes in length and parents and youth will each receive \$30 electronic gift card for each assessment.

Immediately after completing the pretest, parents will be randomly assigned (block by gender and ethnicity) to the eNBP or to a waitlist comparison condition using a computerized program. Parents in the eNBP condition will be sent a link to eNBP and instructed to complete the program over the next 10 weeks. Parents in the WebC will be sent a link to the control web-site and will be instructed to use the material on the website over the next 10 weeks. To reduce attrition across assessments, contact efforts (e.g., address verification requests by email,

contact with non-responders by phone or letter) will be conducted every two months. Parents will receive a \$5 electronic gift card for providing address updates. Three months after the pretest, participants will be sent a link to the posttest assessment.

Phone calls will be made to non-responders. Six months after the posttest, participants will be sent a link to the 6-month follow-up assessment; phone calls will be made to non-responders. Upon completion of the 6-month follow-up survey, parents in the WebC will receive a link to access eNBP. Study procedures will be reviewed by the Quorum Institutional Review Board (IRB). [name] will develop and submit the IRB protocol, with significant input from Drs. [name] and [name].

Conditions. eNBP will consist of 10 modules that teach skills to increase positive family interactions, active listening skills, and effective discipline, and decrease exposure to interparental conflict.

Parents in the WebC will be provided with a link to a website that has been recommended by authoritative experts.

C3.33 Measures. Parents and youth ages 11 to 18 will complete measures of parenting, conflict and children's outcomes. Parents will answer questions about parenting and children's outcomes for each of their children ages 6-18. The timeframe for all measures will be the last month. We will use age and gender norms for the BPM. We selected measures that have been shown to be sensitive to program effects, are appropriate for children 6 to 18, are equivalent across ethnic groups, and have adequate reliability and validity. When possible, we will obtain parent and child report of a construct.

Data Analyses. All data will be managed and processed by project staff to ensure that the data collected are of the highest quality. Block randomization, which improves face validity, precision, and power, will be conducted within parent gender and ethnicity using a random number generator. Power is based on the MPlus simulation program or Optimal Design using $\alpha = .05$ (two-tailed) and power $(1-\beta) = .80$. We will apply intent-to-treat analyses (i.e., including every family who is randomized) to examine program effects. We will perform sensitivity analyses to check the nonresponse mechanism and attrition analyses (i.e., comparing those who stay and those who leave across condition) on the baseline variables to understand the patterns of attrition and then use modern analytical strategies such as multiple imputation (MI) or full information maximum likelihood (FIML) for dealing with ignorable missing data (i.e., missing completely at random [MCAR] or missing at random [MAR]) or the selection model or the pattern mixture model to deal with nonignorable missing data (i.e., missing not completely at random [MNAR]). Thus, we will use the entire randomized sample for hypothesis testing. Confirmatory factor analyses (CFA) will test measurement models for the domains that involve multiple indicators or multiple informants. Such data reduction procedures will serve to reduce measurement errors and consolidate measures into key theoretical constructs. We will examine measurement equivalence across child age (e.g., 6-9, 10-18), gender, and ethnicity. Mplus¹³⁰ will be the primary statistical program for our analyses which can incorporate FIML and MI for handling missing data.

Outcome analyses. We will compare means across condition at post-test and 6-month follow-up using random effects or mixed effects analyses of covariance (ANCOVA) controlling for possible baseline differences. Clusters of children in the same family will be treated as random effects. The 6-month follow-up analyses will assess maintenance or an increase or decrease in effects over time. We will use all of the three assessments and conduct repeated measures random

effects model (i.e., time points nested in individuals and children nested in families) to evaluate the trajectory of program effects. Specifically, we will estimate whether individual trajectories vary from person to person and whether the inter-individual variation is systematically related to condition. In addition to main effects, we are interested in potential differential program effects across baseline conflict, parent gender and ethnicity and child age. Moderation will be tested using the condition by moderator interaction. For significant interactions, we will conduct simple effects analyses to probe the magnitude and direction of the program effects at different levels of the moderator. Depending on the intraclass correlation (ICC), we have power to detect a mean difference with a small effect for the full sample ($d = .25\text{-.29}$; $.36\text{-.41}$ for adolescents [10-18]). For the moderated effects, we have power to detect a small effect for the full sample ($R^2 = 2\%\text{-}3\%$; $4\%\text{-}5\%$ for adolescents [10-18]). Note that the interaction effects in randomized trials are in general small.

For models with limited power, we plan to use bootstrap methods, which improve precision of asymptotic approximations (e.g., confidence interval) or a Bayesian approach, which incorporates prior information to improve estimation, for hypothesis testing. For repeated measures, we have power to detect a small effect for the full sample (i.e., $d = .20\text{-.22}$; $.27\text{-.31}$ adolescents [10-18]). A simulation study shows that mixture modeling with repeated measures provides better power than the traditional ANCOVA.

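### The adolescent detectable effects (d = .36-.41) are a best case: they leave room for at most about 12% youth-specific loss, carry a 10-18 label that does not match youth report (11-18), and predate the cut in sample size

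*Combined protocol and SAP*

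**What the plan says.** Recruitment and Procedures sets the size: the sampling panel "will be used to recruit 360 parents", and "we anticipate there will be 1.5 children/family who are between 6 and 18 years old, giving a total of 540 children". It expects half of these children to be 11 or older, "giving a possible total of 270 adolescent reports".

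The same section describes how a youth report is obtained. "Offspring ages 11-18 whose parents provide permission for them to participate in the assessments will be called by a research specialist", after which the adolescent gives assent (or consent at 18) and receives web links to the assessments. No permission, assent or response rate is given. Measures confirms that youth aged 11 to 18 report for themselves, while parents report on every child aged 6-18.

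Data Analyses fixes the error rates (two-tailed .05, power .80): "Power is based on the MPlus simulation program or Optimal Design using" those values. Outcome analyses then gives d = .25-.29 for the full sample and .36-.41 "for adolescents [10-18"], depending on an ICC whose value is not stated. The moderation figures (4%-5% of variance) and repeated-measures figures (.27-.31) for adolescents carry the same 10-18 label.

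The opening note says that the text is that of the grant application and that "the scope of the trial was modified to have a reduced number of participants and to drop the follow-up assessment". No new sample size or power is given.

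**The concern.** A youth report passes through steps that a parent report does not: the parent's permission, a call to the adolescent, and the adolescent's own assent and web assessments. If the adolescent detectable effect is derived by halving the child sample, almost nothing has been set aside for losses at those steps. The plan itself presents 270 as a ceiling.

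The age label adds doubt about what the figures describe. If they concern youth report, the band should be 11-18. If they concern parent report on children aged 10-18, the plan states no detectable effect for youth report at all, although the opening note presents responses from both children and parents as a feature kept in the modified trial.

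At stake is the reading of a null youth-report result. A reader who trusts .36-.41 would take it as evidence against effects of that size when the trial may have had clearly less than 80% power to find them.

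**Working it through.** **Inputs.** From the documents: two-sided alpha .05; power .80; 360 parents; 1.5 children per family, so 540 children; 50% aged 11 or older, so 270; stated d of .25-.29 and .36-.41. Assumed because not stated: 1:1 allocation, the ICC, attrition, covariate strength and the number of adolescents per family.

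**Formula.** d = 2 × 2.80 × sqrt(V × (1 + (m − 1) × ICC) / N), where 2.80 = 1.96 + 0.84, m is children per family and V collects factors common to both samples (covariate adjustment, common attrition).

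**Reproducing the plan's figures.** They cannot be reproduced uniquely.
- 270 independent reports, no loss: d = .341, below the stated range.
- 270 reports, m = 1.5, no loss: .36-.41 needs ICC of about .23 to .89.
- 10% loss in both samples (243 of 270; 486 of 540), m = 1.5, ICC 0 to .6: .359-.410 for adolescents and .254-.290 for the full sample. All four stated figures are matched.

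**What the ratio shows.** With equal m, everything except N cancels, so adolescent share = (d full / d adolescent)².
- Lower ends: (.25/.36)² = .482; with two-decimal rounding, .451 to .516.
- Upper ends: (.29/.41)² = .500; with rounding, .472 to .531.
- Both together: 47% to 52%.

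Against the plan's 50%, the lowest value allows .472/.50 = .94, or about 6% extra youth loss.

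**Unequal cluster size.** Families may have fewer than 1.5 adolescents each. Scanning m for adolescents from 1.0 to 1.5, ICC from 0 to 1 and a common V, values of m of 1.25 or less cannot match the stated ranges. Among the combinations that do, youth-specific loss never exceeds about 12%.

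**Repeated-measures pair.** (.20/.27)² and (.22/.31)², with rounding, jointly give 50% to 54%, so no extra youth loss appears there either.

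**Age band.** A 10-18 group is the 11-or-older group plus the 10-year-olds, so it should exceed 50% of the children. An implied share of 47%-52% fits 11 or older more naturally, though rounding does not exclude a slightly larger band.

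**Illustration at 360 families.** If a further fraction r of the implied youth base is observed, the stated d is divided by sqrt(r). The rates are assumed.

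| r | Reports, if the base is 270 | Detectable d | Power at the stated d |
|---|---|---|---|
| 90% | 243 | .38-.43 | 76% |
| 80% | 216 | .40-.46 | 71% |
| 70% | 189 | .43-.49 | 65% |

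Fewer families worsen each row: if the number falls to a fraction f of 360, d is divided by sqrt(f) as well. The documents do not give f.

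**The case against.** The best counter-argument is that no sentence ties .36-.41 to the 270 reports or to youth report. Parents report on all children aged 6-18, Data Analyses uses 6-9 and 10-18 as its example of an age split for measurement equivalence, and child age is a planned moderator. So 10-18 may be a deliberate parent-report subgroup. This stands as a possible reading. It moves the gap without closing it: the plan would then give no youth-report figure, and the implied share would be low for that band.

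Three stronger readings are tempting and are not supported.
- A reader might infer that all 270 reports were counted as observed. The common 10% loss shown above fits equally well.
- A reader might infer that the adolescent figures are exactly the square root of 2 times the full-sample ones. The printed ratios are 1.44 and 1.41, and the repeated-measures pair .27/.20 stays below 1.414 even with rounding (at most .275/.195 = 1.410).
- A reader might infer that the 10-18 band supplies no youth reports. Only the 10-year-olds do not.

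Two cautions on size also stand. Attrition may already be inside the stated figures, so multiplying in a separate posttest retention rate could count it twice; the table does not do so. And FIML, multiple imputation or a multi-informant factor model could recover some of the information lost with a missing youth report, so the simple scaling may overstate the loss for constructs that combine informants.

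**Conclusion.** The point holds as one about an undocumented and optimistic basis, not as a proven arithmetic error. The stated figures imply an adolescent base of about half the child sample, with at most about 12% allowed for youth-specific loss. Read as youth-report power, .36-.41 is a best case even at 360 families, and since participant numbers were later reduced it does not describe the modified trial. At assumed youth rates of 90% to 70%, the detectable effect at 360 families runs from .38-.43 to .43-.49.

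The 12% bound rests on the normal approximation, 1:1 allocation, an ICC and covariate strength common to both samples, and two-decimal rounding. The illustrated sizes rest on assumed rates, because the documents give none. The conflict between 10-18 and 11-18 needs no assumption: the power text names no informant, so a reader cannot tell which reports the figures cover.

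**What to change.** 1. Restate the adolescent detectable effects for the modified number of families, as a range over assumed rates of permission, assent and response among youth.
2. Beside each adolescent figure, give the N, the informant, the ICC, the covariate assumption and any attrition already included, so that loss is not counted twice.
3. Reconcile the 10-18 label with the 11-18 youth-report range. Alternatively, label a figure as parent report on ages 10-18 and add a separate youth-report figure for 11-18.
4. Treat the moderation figures in the same way. The repeated-measures figures need it too, and they belong to a plan with three assessments, whereas the follow-up has been dropped.

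This takes recalculation and wording only; recruitment, measures and analysis methods are unchanged. The downside is a less favourable stated detectable effect for adolescents.

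### Attrition is compared on baseline variables only and eNBP use has no stated role, so MI or FIML may overstate the intent-to-treat effect if low users also tend to miss the posttest

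*Combined protocol and SAP*

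**What the plan says.** The Data Analyses section promises an analysis by assignment: "We will apply intent-to-treat analyses (i.e., including every family who is randomized) to examine program effects". On missing data, one sentence carries the plan:

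- It opens with a check: "We will perform sensitivity analyses to check the nonresponse mechanism". Neither the variables nor the method is given.
- It adds "attrition analyses (i.e., comparing those who stay and those who leave across condition) on the baseline variables to understand the patterns of attrition".
- If missingness is ignorable, the tools are "multiple imputation (MI) or full information maximum likelihood (FIML) for dealing with ignorable missing data". The variables in those models are not listed.
- If it is not, the sentence continues "or the selection model or the pattern mixture model to deal with nonignorable missing data". No rule says when to switch, and no MNAR assumption is stated.

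On programme use, Recruitment and Procedures says: "Parents in the eNBP condition will be sent a link to eNBP and instructed to complete the program over the next 10 weeks". The Conditions section gives 10 modules. Neither section mentions recording how many are done. Assessment does not depend on use: "Three months after the pretest, participants will be sent a link to the posttest assessment", and non-responders are phoned. The opening paragraph says that the follow-up assessment was dropped, which leaves the posttest as the only assessment after randomisation.

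**The concern.** MI and FIML are valid under MAR given the variables in the model. With condition and baseline alone, an eNBP parent who did one module and one who did all 10 are interchangeable if their pretests match. In a self-paced web programme, losing interest in the modules and ignoring the posttest link may well go together. If so, eNBP responders over-represent users, and the missing outcomes of low users are predicted from them. The result drifts from the effect of being assigned eNBP towards the effect in those who used it.

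A baseline comparison cannot reveal this, because use happens after baseline. Stayers and leavers could look balanced, missingness could be called ignorable on that evidence, and the analysis could end with MI or FIML alone. With the follow-up gone, no later assessment can inform a missing posttest. Under the waitlist design of the opening paragraph, the control arm has no programme to abandon, so this mechanism would act in one arm.

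**Working it through.** **The plan's own figure.** Outcome analyses states a detectable d of .25 to .29 for the full sample. With 540 children split 1:1 (270 per arm; the ratio is assumed), 1.5 children per family, two-sided alpha .05 and power .80:

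d = (1.960 + 0.842) × √(2/270) × √(1 + 0.5 × ICC) = 0.241 × √(1 + 0.5 × ICC).

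The ICC is not stated. A value of .15 gives .250 and .90 gives .290, so the range reproduces with no allowance for dropout. It predates the cut in sample size and serves here only as a scale: the true intent-to-treat effect is set at .25.

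**Inputs.** The documents give no rate of programme use or posttest response, so all of these are assumptions: s = share of eNBP parents who stop early; r_s = their posttest response; r_c = .90, the response of completers; k = stoppers' benefit as a fraction of the completers' effect e. Control missingness is taken as unrelated to outcome given baseline.

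**Formulas.**

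- Share of completers among eNBP responders: p = (1−s)r_c / [(1−s)r_c + s·r_s].
- Completers' effect: e = .25 / [(1−s) + k·s].
- Gap between completers and stoppers in mean outcome: Δ = e(1−k).
- Bias of a MAR fit on condition and baseline: [p − (1−s)] × Δ.

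**One case in full** (s = .30, r_s = .40): p = .63/(.63 + .12) = .84, so the excess share of completers is .84 − .70 = .14.

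- No benefit to stoppers: e = .25/.70 = .357; bias = .14 × .357 = .050; estimate .300 (+20%).
- Half benefit: e = .25/.85 = .294; Δ = .147; bias = .14 × .147 = .021; estimate .271 (+8%).

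| s | r_s | p | Estimate, no benefit | Estimate, half benefit |
|---|---|---|---|---|
| .20 | .60 | .857 | .268 (+7%) | .258 (+3%) |
| .30 | .40 | .840 | .300 (+20%) | .271 (+8%) |
| .50 | .40 | .692 | .346 (+38%) | .282 (+13%) |

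A simulation of the no-benefit cases with n = 400,000 gave .262, .301 and .344, against full-data values of .246, .252 and .249. Adding stop status to the model gave .246, .250 and .245.

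**When the bias is absent or reversed.** If r_s = r_c, then p = 1−s and the bias is zero. If non-users would differ from users by δ even without the programme, and gain nothing from it, then Δ = e − δ. A second simulation used 180 per arm, pre-post correlation .6, an effect of .30 in users, 30% non-users, and posttest missing in 10% of users, 50% of non-users and 15% of controls. The true intent-to-treat effect is .70 × .30 = .21.

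| δ (SD) | MAR without use | MAR with use |
|---|---|---|
| −.3 | .271 | .207 |
| 0 | .241 | .209 |
| +.15 | .224 | .208 |
| +.3 | .210 | .210 |
| +.4 | .200 | .211 |

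The overstatement vanishes once non-users' better prognosis equals the programme effect, and reverses beyond that. In these runs, use fully explains the missingness in the eNBP arm, which is why adding it removes the bias.

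**The case against.** The strongest reply is that the same sentence already provides for nonignorable missingness, through a check of the nonresponse mechanism and two MNAR model families. A control-based imputation is itself a pattern mixture analysis. This stands in part: the plan names the right class of method. But the methods are alternatives without a trigger or a stated assumption, observed data cannot tell MAR from MNAR, and the only diagnostic whose variables are given is the baseline comparison.

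A reader might infer three stronger things that the documents do not support.

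- *That the plan excludes programme use.* It does not. The limit to baseline variables applies to the attrition comparison; the contents of the MI or FIML model are simply not listed. The gap is silence.
- *That MI or FIML fills in everyone who stopped the programme.* It fills in missing outcomes only. A parent who stops but answers the posttest counts with the observed value, as intent to treat requires.
- *That the reported effect will be inflated.* Direction and size depend on rates that the documents do not give.

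Two further points have some force. The assessment payments, the phone calls to non-responders and the contact efforts every two months all work against a wide response gap, though they need not close it. And youth aged 11 to 18 report separately, so a multi-informant model could use one informant's posttest to inform the other's. That does not help younger children, or families in which both are missing.

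**Conclusion.** The concern holds conditionally. The attrition comparison is tied to baseline variables, and no use of eNBP engagement data is stated anywhere. If low use predicts a missing posttest, MI or FIML on condition and baseline may overstate the intent-to-treat effect, and the planned baseline comparison could not show it.

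Under the assumed rates, the overstatement runs from about 3% (20% stop, 60% of them respond, half benefit) to 38% (50% stop, 40% respond, no benefit): .01 to .10 on a true effect of .25. This rests on a response gap between completers and stoppers, on stoppers gaining less, and on their having no materially better prognosis. Without the first, the bias is zero; with a better enough prognosis, it vanishes or reverses. The listed MNAR models reduce the concern without settling it. This is a worthwhile and cheap improvement, not a proven bias in the result.

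**What to change.** 1. Record modules completed for each eNBP parent. This assumes that the programme site can log it, which the documents do not say.
2. Add modules completed to the stayer/leaver comparison within the eNBP arm.
3. Include it as an auxiliary variable for the eNBP arm in MI or FIML, imputing by arm. Do not make it a covariate in the outcome model, because it arises after randomisation.
4. Prespecify one pattern mixture sensitivity analysis that is always run, whatever the nonresponse check shows: impute eNBP non-responders with few or no modules completed from the control arm. Define few in advance.

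The cost is a usage export and a little model code. The interval will be slightly wider and the estimated effect possibly smaller. If few early stoppers answer the posttest, which is more likely in the reduced sample, the auxiliary variable carries little information and the sensitivity analysis matters more.

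### The follow-up was dropped and the sample cut, but the analysis plan still needs a third assessment and quotes detectable effects from the grant design, with no reduced sample size stated

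*Combined protocol and SAP*

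**What the plan says.** The Study Protocol paragraph discloses that "The protocol is described as it was presented in the grant application", and then that "the scope of the trial was modified to have a reduced number of participants and to drop the follow-up assessment". It gives no new sample size.

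The rest of the document keeps the larger, longer design:

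- **Sample (Recruitment and Procedures).** Qualtrics "will be used to recruit 360 parents from a nationally representative sample". At 1.5 children per family this is described as "giving a total of 540 children", and with half of them aged 11 or older as "giving a possible total of 270 adolescent reports".
- **Schedule (Recruitment and Procedures).** "Six months after the posttest, participants will be sent a link to the 6-month follow-up assessment". Release of the program to control parents depends on the same survey: "Upon completion of the 6-month follow-up survey, parents in the WebC will receive a link to access eNBP".
- **Analysis (Outcome analyses).** The plan compares condition means at post-test and at 6 months and uses the 6-month data to judge whether effects last, grow or fade. It continues: "We will use all of the three assessments and conduct repeated measures random" effects models, meant to show whether individual trajectories differ and whether condition explains the differences.
- **Power (Outcome analyses).** Detectable effects at 80% power and two-sided alpha .05 are d .25-.29 (adolescents .36-.41) for a mean difference, R-squared 2-3% (4-5%) for moderation, and d .20-.22 (.27-.31) for repeated measures.

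**The concern.** The document announces a change of design but gives no analysis plan for the changed trial. Two planned questions, the 6-month comparison and maintenance, depend on an assessment that no longer takes place. The trajectory model is written for three assessments and has two. The text does not say which analysis now carries the trial's conclusion, so a reader cannot tell which result was specified in advance as the outcome analysis.

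The power statement has the same gap. It sits beside the grant sample, and nothing shows that any of its figures holds for the smaller trial. A null result could not be judged against it. The schedule also ties control-arm access to a survey that has been dropped, so those passages contradict each other.

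**Working it through.** **1. The sample.** 360 x 1.5 = 540 children, and 540 x 0.5 = 270 adolescents. Both match the document. The power text labels adolescents 10-18, while adolescent reports are from ages 11-18.

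**2. The printed mean-difference effects.** Alpha and power are from Data Analyses and 1.5 children per family is from Recruitment and Procedures. Equal allocation, the ICC, no attrition, and 1.5 adolescents per family are assumptions.

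d = (1.960 + 0.842) x sqrt[2 x (1 + 0.5 x ICC) x (1 - rho^2) / n per arm], where rho is the pre-post correlation. With no covariate adjustment, rho = 0:

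| Sample | n per arm | ICC .2 | ICC .9 | Printed |
|---|---|---|---|---|
| Full | 270 | .253 | .290 | .25-.29 |
| Adolescents | 135 | .358 | .411 | .36-.41 |

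The ICC range was chosen to fit, because the plan gives none. With 10% attrition, an ICC range of about 0 to .60 fits both rows instead.

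**3. The other printed effects.** For moderation, f2 = 7.85 / n_eff, with n_eff = children / (1 + 0.5 x ICC) and R-squared = f2 / (1 + f2). At ICC .2-.9 this gives 1.6-2.1% (printed 2-3%), and 3.1-4.0% for adolescents (printed 4-5%). That is a rough match only. The repeated-measures figures could not be reproduced. The only repeated-measures model in the plan is the three-assessment one.

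**4. Smaller samples without adjustment.** The detectable effect scales by sqrt(360 / parents). The parent numbers are illustrative.

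| Parents (assumed) | Factor | Full | Adolescents | Power at printed effects |
|---|---|---|---|---|
| 240 | 1.22 | .31-.36 | .44-.50 | 63% |
| 120 | 1.73 | .43-.50 | .62-.71 | 37% |

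**5. What baseline adjustment could recover.** If the ICC is unchanged by adjustment, the number of parents that restores the printed range is 360 x (1 - rho^2). With an assumed 20% loss to post-test, divide by 0.8.

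| rho (assumed) | No loss | 20% loss |
|---|---|---|
| .3 | 328 | 410 |
| .5 | 270 | 338 |
| .7 | 184 | 230 |

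At rho .3 with 20% loss, no sample below 360 would do. Below break-even the printed .25-.29 is optimistic. For 240 parents at rho .5 the multiplier is sqrt(1.5 x 0.75), giving .27-.31. For 120 parents at rho .7 it is sqrt(3 x 0.51), giving .31-.36. Both are without attrition.

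**6. What two assessments can identify.** Take a linear growth model with random intercept, slope and covariance at family and child level, plus a residual: 7 parameters. With one score at 0 and 3 months there are 6 moments (variances and covariances within a child and between siblings), and the rank is 6. The unidentified direction is zero on all three family parameters. On child intercept variance, slope variance, covariance and residual it is -1, -0.222, +0.333 and +1. So only the within-family child part is lost. Fixing the child covariance at zero gives rank 6 of 6. Adding the 9-month point (6 months after post-test) gives rank 7 of 7.

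**The case against.** The strongest reply is that the document discloses the mismatch at the outset. The reader is told that the body is grant text and that the follow-up is gone, so the 6-month elements fall away. It is right that nothing is hidden. But the disclosure supplies no replacement sample size, power or analysis. The body was also partly updated, since Recruitment and Procedures already names the waitlist comparison, so a reader cannot treat all of it as archival.

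Four further objections narrow the point, and they stand:

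- **The power match is fitted.** The ICC range was chosen to reproduce the printed figures, and no covariate was used although ANCOVA is planned. The adolescent match also needs 1.5 adolescents per family. If half the families have one child and half two, with ages independent, families with any adolescent average 0.75 / 0.625 = 1.2. The largest d, at ICC 1, is then 2.802 x sqrt(2 x 1.2 / 135) = .374, short of .41. A strong covariate with fewer children could give the same printed effects. The link to the grant sample therefore rests mainly on the document's own statement that the body is grant text.
- **Trajectory variation is not always beyond reach.** Measures and Data Analyses foresee several informants and confirmatory factor models. Two indicators per wave with invariant loadings and uncorrelated residuals identify the change variance (rank 8 of 8). If residuals of the same indicator correlate across waves, two indicators are not enough (rank 9 of 10). The plan specifies no such growth model.
- **Repeated measures need not be abandoned.** The average condition-by-time effect is estimable from two assessments.
- **The covariate is not spelled out.** The plan says only that baseline differences will be controlled for. Using the pretest score is a natural reading, but not a stated one.

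**Conclusion.** The plan as written does not fit the trial it describes. The 6-month comparison and the maintenance question have no data. The three-assessment model cannot run in its stated form, and with a single score per wave it cannot show variation between children in their trajectories without an added constraint or a multiple-indicator model. Random assignment, the intent-to-treat principle, the post-test comparison, the moderation tests, the average condition-by-time effect and the family-level slope variance are untouched.

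A reader might infer that the reduced trial is underpowered. The documents do not support that, because the reduced N, ICC, pre-post correlation and attrition are all unstated. Depending on them, the printed range could still hold or fall well short. What can be said is that none of the printed effects is shown to apply. A reader might also infer that no repeated-measures analysis remains possible, or that the treatment estimate is biased. Neither follows.

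The textual contradiction and the lack of a reduced N are certain. The numerical illustrations rest on the assumed values shown.

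**What to change.** 1. Remove the 6-month comparison and the maintenance question.
2. Name the post-test mixed-effects ANCOVA as the outcome analysis, specifying the pretest score as covariate and a family random effect. Keep the moderation tests.
3. Drop the three-assessment trajectory model, or restate it for two assessments as a condition-by-time effect. Make no claim about individual trajectory variation unless a specified multiple-indicator model supports it.
4. State the reduced numbers of parents, children and adolescents. Restate the mean-difference and moderation detectable effects at those numbers, with the assumed ICC, cluster size (separately for adolescents), pre-post correlation and attrition.
5. Withdraw the repeated-measures detectable effects, or recompute them for two assessments.
6. Limit conclusions to the post-test effect.
7. Reconcile the assessment schedule and the control-arm access step in Recruitment and Procedures with the dropped follow-up.

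The cost is rewording, a short recalculation and possibly less favourable stated figures. No data are lost, because the third assessment was already dropped.
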